Although no formal drug interaction studies have been performed, tiotropium bromide has been used concomitantly with other drugs, including sympathomimetic bronchodilators, methylxanthines, oral and inhaled steroids, antihistamines, mucolytics, leukotriene modifiers, cromones, and anti-IgE treatment without clinical evidence of drug interactions [see SPC for Spiriva Respimat 2.5 µg; <https://www.medicines.org.uk/emc>]. Use of long-acting beta agonists or inhaled corticosteroids has not been found to alter the exposure to tiotropium. The co-administration of tiotropium bromide with other anticholinergic containing drugs has not been studied and therefore is not recommended. Overdose of tiotropium may lead to undesired anticholinergic effects. However, single inhaled dose of up to 340 µg tiotropium bromide in healthy volunteers caused no systemic anticholinergic adverse effects [see SPC for Spiriva Respimat 2.5 µg; <https://www.medicines.org.uk/emc>]. Additionally, no relevant adverse effects, beyond dry mouth/throat and dry nasal mucosa, were observed following 14-day dosing of up to 40 µg tiotropium inhalation solution in healthy volunteers with the exception of pronounced reduction in salivary flow from day 7 onwards [see SPC for Spiriva Respimat 2.5 µg; <https://www.medicines.org.uk/emc>].

Tiotropium in preclinical studies

According to SPC for Spiriva Respimat 2.5 ug [see <https://www.medicines.org.uk/emc>], in preclinical safety studies, many effects observed in animals - including reduced food consumption, inhibited body weight gain, dry mouth and nose, reduced lacrimation and salivation, mydriasis and increased heart rate - can be explained by the anticholinergic properties of tiotropium bromide. In repeated dose toxicity studies following effects were also observed: mild irritancy of the respiratory tract in rats and mice evinced by rhinitis and epithelial changes of the nasal cavity and larynx, and prostatitis along with proteinaceous deposits and lithiasis in the bladder in rats. In juvenile rats exposed from postnatal day 7 to sexual maturity, the same direct and indirect pharmacological changes were observed as in

the repeat-dose toxicity studies as well as rhinitis. No systemic toxicity was noted and no toxicologically relevant effects on key organ development were seen.

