In Clinical Trial Registries (see www.clinicaltrials.gov and www.clinicaltrialsregister.eu), there are altogether 7 clinical trials on tiotropium as add-on therapy in asthma in children: one study including children aged 1 to 5 years (trial number: NCT01634113), three studies including children aged 6 to 11 years (trials: NCT01634139, NCT01634152, NCT01383499), and three studies including adolescents (trials: NCT01257230, NCT01122680, NCT01277523). Results on efficacy and safety issues have recently been published for asthmatic adolescents (trials number: NCT01122680, NCT01257230) [Vogelberg et al. 2014, Hamelmann et al. 2016], and children aged 6 to 11 years (trial number: NCT01383499) [Vogelberg et al. 2015], and children aged 1 to 5 years (trial number: NCT01634113) [Vrijlandt et al. 2018]. In addition, tiotropium has been investigated in children suffering from cystic fibrosis [Konstan et al. 2015, Ratjen et al. 2015], and in children with postinfectious bronchiolitis obliterans [Teixeira et al. 2013].

Safety of tiotropium in clinical studies in adults

The main side effect of tiotropium reported in clinical studies is dryness of the mouth in <2% of patients [Befekadu et al. 2014, Kerstjens et al. 2012, Kerstjens et al. 2015]. In a 48-week

intervention with tiotropium in severe asthma poorly controlled with standard combination therapy in 912 adults, drug-related adverse events were similar in the tiotropium group (5.7%) and in the placebo group (4.6%). Serious adverse events were reported for 8.1% of the patients in the tiotropium group and 8.8% in the placebo group; drug-related cardiac events being rare (0.4%), including no deaths [Kerstjens et al. 2012]. In a recent report combining data on two 24-week trials on tiotropium in moderate asthma, serious adverse events occurred in 2% of the 2100 patients included [Kerstjens et al. 2015]. Incidence of serious adverse events was similar between the intervention groups, and none of the life-threatening serious adverse events occurring in four patients was regarded as drug-related, and there were no deaths [Kerstjens et al. 2015].

Efficacy and safety of tiotropium in children

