The preliminary results of the tiotropium trial including asthmatic children from age of 1 year on (trial number: NCT01634113) [Vrijlandt et al. 2018], showed no differences in safety profiles between those receiving tiotropium 5 µg, those receiving tiotropium 2.5 ug, and those receiving placebo. No serious adverse events occurred in either of the tiotropium groups during the 12-week intervention period, whereas 3 of the 34 children receiving placebo experienced a serious adverse event (i.e. appendicitis, bronchopneumonia and exacerbation of asthma, viral upper respiratory infection), requiring hospital admission. Among other adverse events, there were no undesirable anticholinergic effects, or no differences in occurrence of adverse events between the intervention groups [Vrijlandt et al. 2018].

In addition, an earlier clinical trial on a short-acting non-selective anticholinergic agent, ipratropium bromide, in 25 children aged 5 to 15 years with severe acute asthma, found no significant differences in side effects between the study groups [Reisman et al. 1988]. Moreover, there is a recent report on tiotropium in cystic fibrosis, including 24 children aged 5 to 11 years, and 24 patients aged 12 years or older [Konstan et al. 2014]. Only two of these patients with cystic fibrosis experienced a serious adverse event, neither of which was considered drug-related [Konstan et al. 2014].

OBJECTIVE

The primary AIM of the study is

- 1) to find out the effect of intermittent tiotropium bromide and salbutamol as needed (TBS) versus intermittent fluticasone propionate and salbutamol as needed (FPS), or solely, salbutamol as needed (SA) on episode-free days in infants and toddlers with recurrent episodes of wheeze and/or shortness of breath.

Episode-free days are defined as those days during which there are no symptoms of wheeze and/or shortness of breath, no unscheduled medical visits for wheeze and/or shortness of breath, and no use of rescue or supplementary controller medications [Guilbert et al. 2006].

The secondary AIMS of the study are

to find out the effect of TBS versus FPS or SA treatment on

- 1) number of unscheduled physician visits for episodes of wheeze and/or shortness of breath,
- 2) need for bronchodilative medication,
and to evaluate
- 3) the safety of TBS versus FPS or SA treatment by paying attention to possible adverse events during treatment

in infants and toddlers with recurrent episodes of wheeze and/or shortness of breath.

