The parents are taught to keep diary on wheeze and shortness of breath, and on the use of rescue and intervention medication. The use of medications is controlled by measuring weights of the inhalators at the end of the 48-week intervention. After the 48-week intervention period, medication for episodes of wheeze and shortness of breath will be planned individually and the patients are remitted back.

Control phone calls by a research nurse will take place at 4, and 8 weeks from the beginning of the intervention. The control visits will take place at 12, 24, 36, and 48 weeks from the beginning of the intervention. In all cases, the first (week 0) and last (week 48) visits are to be organized at HUH Skin and Allergy Hospital. For those subjects living in Helsinki, the control visits at 12, 24, and 36 weeks will take place at HUH Skin and Allergy Hospital, and for those living in surrounding municipalities of Helsinki, the control visits (at 12, 24, and 36 weeks) will take place at a local hospital (Jorvi, Porvoo, or Hyvinkää), i.e. nearest hospital of the living place of the study subject.

Adverse events requiring unscheduled medical attendances, as well as serious adverse events requiring hospital admission are to be charted. In case the study patient is diagnosed a chronic illness needing regular controls and physician care, the investigator will evaluate the situation and considers, case by case, a withdrawal of the patient from the study. However, hospitalization for wheezing or shortness of breath, or administration of drugs other than the interventional ones are not considered as indications for the discontinuation of the study, as these occasions are regarded as normal occurrences in early childhood wheezing illnesses. Per oral or inhalant corticosteroids may be used in any of the study groups as additional medications if they meet the criteria stated in the Finnish Current Care Guidelines for asthma in children [see <http://www.kaypahoito.fi/web/english/home>].

In case of the discontinuation, wheezing episodes of the study children will be treated according to the Finnish Current Care Guidelines for asthma in children [see <http://www.kaypahoito.fi/web/english/home>].

Blood and urine samples

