A venous blood sample is a part of the routine diagnostic evaluation and is drawn from all children (5-15 ml of blood, <1% of the circulating blood volume) during the first visit, and at the 48-week visit. In addition, a urine sample is collected during the first visit, and at the 48-week visit. Following parameters are to be analysed: total blood cell count, serum allergen-specific immunoglobulin E concentrations for a mixture of inhalant and food allergens (Phadiatop combi®). In addition, serum 1-2 ml and urine 10 ml are taken for storage for analysis of immunological markers in future.

Handling of data

Detailed personal information on the study patients is collected by interviewing the caregivers during the study visits and by phone calls by study investigators and registered study nurses, and by collecting data from patient files in medical records. No data enabling identification of the patient is included in the case report forms or electronic files including the study data. IBM SPSS version 22.0 is used for electronic handling of the study data, including saving and analysing study material in an electronic form. The case report forms are saved in lockers in locked storage rooms. Only certain named investigators, a study monitor, and study nurses have access to the case report forms and the electronic study data. Whenever any changes are performed in the case report forms, the changes are to be verified by a signature. In case the changes are made in electronic data, a new file is to be created to document changes in the data.

Discontinuation of the study leads to the intention-to-treat analysis of the collected case-specific data.

The study files and data are preserved until the study children reach school age, in order to give an opportunity for a final evaluation of the study patients' respiratory state. However, such long-term evaluations reaching school age are out of the scope of the present research protocol.

Insurances

Injuries related to the actions of investigating physicians or nurses, or injuries related to the study investigations or measurements are to be covered with a patient insurance.

Pharmaceutical injuries insurance covers possible unexpected study drug-related adverse events.

Ethical considerations

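### The only adverse-event recording rule in the text covers medically attended and serious events, while safety aim 3 has no such limit: specify capture of milder events, or limit the safety conclusion

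*Combined protocol and SAP*

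**What the plan says.** The OBJECTIVE section lists as third secondary aim to evaluate "the safety of TBS versus FPS or SA treatment by paying attention to possible adverse events during treatment". TBS, FPS and SA are the intermittent tiotropium, intermittent fluticasone and salbutamol-only groups. The aim sets no threshold of severity or medical attendance.

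The section Study population and study design gives the recording rule: "Adverse events requiring unscheduled medical attendances, as well as serious adverse events requiring hospital admission are to be charted". The same section describes the diary: "The parents are taught to keep diary on wheeze and shortness of breath, and on the use of rescue and intervention medication". It also sets the contacts: "Control phone calls by a research nurse will take place at 4, and 8 weeks from the beginning of the intervention", followed by visits at weeks 12, 24, 36 and 48.

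Handling of data adds a general channel: "Detailed personal information on the study patients is collected by interviewing the caregivers during the study visits and by phone calls", together with data from medical records. The STATISTICAL ANALYSIS PLAN puts every participant in the safety analyses but does not say which events are analysed.

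On what is already known, the background on adult safety states: "The main side effect of tiotropium reported in clinical studies is dryness of the mouth in <2% of patients". For a 12-week trial at ages 1 to 5 years, the background reports: "Among other adverse events, there were no undesirable anticholinergic effects, or no differences in occurrence of adverse events between the intervention groups".

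**The concern.** The aim speaks of adverse events in general, and the recording rule reaches only those that led to an unscheduled attendance or an admission. Dry mouth, the effect the protocol itself puts first for tiotropium, is one for which a caregiver may well not seek care. If the trial is run by the rule alone, such an event is not charted, and an absence of reported dry mouth would reflect the rule as much as the drug.

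What is at stake is the wording of the safety conclusion. A reader of the results could take it to cover all adverse events when the data cover the attended and serious ones. The primary endpoint, the sample size and the other secondary aims are not touched.

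**Working it through.** **The text.** Each place where adverse-event capture could be specified:

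| Place | What it specifies |
|---|---|
| OBJECTIVE, secondary aim 3 | Adverse events during treatment, no threshold |
| Study population and study design, recording rule | Attended events; serious events needing admission |
| Same section, diary | Wheeze, shortness of breath, medication use; no adverse-event item |
| Same section, calls and visits | Timing only; no adverse-event content |
| Handling of data | Caregiver interviews and record review; no adverse-event question named |
| STATISTICAL ANALYSIS PLAN | Who is in the safety analyses, not which events |

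The interviews are a channel through which milder events could be asked about, but nothing says that they are. Record review would mainly find attended events.

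**The plan's own figure.** The stated 64 per group reproduces: 2 × (1.960 + 0.842)² × 27² / 15² = 50.9, rounded up to 51, and 51 / 0.80 = 63.75, rounded up to 64. It concerns the primary endpoint, and nothing below changes it.

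**Inputs for the size of the gap.** 65 children per group (Study population and study design); drop-out of 20% (STATISTICAL POWER OF THE STUDY), giving 65 × 0.80 = 52; dry mouth below 2% (adult heading). The documents give no rate for ages 6 to 35 months, so 2% is used as a ceiling, and 1% and 0.5% are assumptions. Every case is taken as detected and recorded.

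Chance of at least one case in the TBS group = 1 − (1 − p)^n:

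| True rate p | Expected cases, 65 × p | n = 65 | n = 52 |
|---|---|---|---|
| 2% | 1.30 | 73% | 65% |
| 1% | 0.65 | 48% | 41% |
| 0.5% | 0.33 | 28% | 23% |

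The n = 52 column gives no credit for partial follow-up.

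**Precision with full recording.** For 0/65 the exact upper 95% limit is 1 − 0.025^(1/65) = 5.5%. For 1/65 the exact 95% CI is 0.04% to 8.3%. One case against none gives a risk difference of 1/65 = 1.5% (Newcombe 95% CI −4.2% to 8.2%).

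**Testing.** Three cases, all in one group, give a three-group Fisher p of 3 × (65 × 64 × 63) / (195 × 194 × 193) = 0.108. Four cases, all in one group, give 0.108 × 62/192 = 0.035. With true rates of 2%, 0% and 0%, significance at 0.05 therefore needs at least four TBS cases: 1 − (0.269 + 0.357 + 0.233 + 0.100) = 0.041. With 2%, 1% and 1%, full enumeration gives 1.6%. Better recording would add description, not a usable test.

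**Recall.** The gaps between contacts are 4, 4, 4, 12, 12 and 12 weeks.

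**The case against.** The strongest reply is that an attendance threshold is a legitimate design choice. The aim is loosely worded and promises no rate of mild events, so the recording rule can be read as its working definition. Attended events are also less prone to bias here. No masking is described, dryness overlaps with the respiratory infection that triggers a treatment course, and children aged 6 to 35 months report little themselves. All of that stands. It is a reason to keep attended events as the main safety summary and to say so in the aim; it does not make the aim and the rule match.

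Three stronger readings are tempting, and the documents do not support them.

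- A reader might infer that the trial *cannot* describe milder events. The rule does not say that nothing else may be charted, caregivers are interviewed, and the case report forms are not supplied. What can be said is that such capture is not specified.
- A reader might add mild constipation as a missed drug effect, since the exclusion criterion removes only constipation needing regular medication or a structural gut defect. The background names constipation only among serious anticholinergic effects, none of which was reported in the adolescent studies it describes, so the documents do not present the mild form as a tiotropium effect.
- A reader might infer that an important harm is being hidden. The 1-to-5-year trial reported no anticholinergic effects. In healthy volunteers, no relevant effects "beyond dry mouth/throat and dry nasal mucosa, were observed following 14-day dosing of up to 40" µg apart from a marked fall in salivary flow; that is 40/5 = 8 times the 5 µg given in this trial. These data do not cover ages 6 to 11 months or 48 weeks of intermittent courses, so a count would still add something, but they give no ground for alarm.

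A remedy that asked only about anticholinergic effects would also be open to objection, because it would concentrate ascertainment on one group.

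**Conclusion.** The mismatch is real and its practical effect is small. By the rule as written, the trial can report on medically attended and serious adverse events; it is not set up to say how often milder ones occurred. At the adult ceiling of 2%, complete recording would be expected to show about one TBS case of dry mouth, with a 65% to 73% chance of any case at all and power of at most 4.1% in the two scenarios examined.

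These figures are upper values for what better recording could show. They assume that every case is noticed and recalled, and that a rate from an adult heading bounds the rate in infants and toddlers. The conclusion on the text assumes that the case report forms contain no questions on milder events. If they do, one sentence in the protocol closes the point.

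**What to change.** (a) For follow-up still to come, ask caregivers in all three groups the same short, neutral adverse-event questions at the contacts already scheduled (weeks 4, 8, 12, 24, 36 and 48). Cover known effects of all the study drugs, not only anticholinergic ones. Flag each event as medically attended or not, report the two separately by group as counts with 95% CIs, keep attended events as the main safety summary, and report exposure under each capture rule.

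(b) For follow-up already completed, or if (a) is not adopted, limit aim 3 and the safety conclusion to medically attended and serious adverse events.

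Cost of (a): a few questions at six existing contacts, a sentence in the SAP, more minor events to tabulate, and possibly an amendment notification to the medicines agency and the ethics committee. Recruitment began in April 2016 and this version cites a 2018 publication, so some children may already have finished their 48 weeks, and capture would differ by calendar time. Differential reporting, overlap with infection symptoms and recall over 12-week gaps would remain. Cost of (b): wording only. Neither changes the sample size, the significance level or the primary endpoint.

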During the first three years of life, up to 30% of all children suffer from episodic wheeze or shortness of breath [Martinez et al. 1995, Skytt et al. 2012], i.e. asthmatic bronchitis, usually induced by viral respiratory infections. The condition causes significant burden to the affected children and their families, including need for acute health care visits, hospitalizations, and costs related to parents' days off from work. However, early childhood wheezing is rarely associated with eosinophilic inflammation of the airways seen in asthma [Saglani et al. 2005], and only one third of these infants and toddlers with wheezing will actually develop asthma [Martinez et al. 1995, Skytt et al. 2012]. Because the condition is very heterogeneous, short-acting beta-agonists are recommended as a monotherapy for symptoms unless there are at least four physician-confirmed episodes of wheeze or shortness of breath, or three episodes plus risk factors according to the modified asthma predictive index [Guilbert et al. 2004] criteria [Finnish Current Care Guidelines for Lower respiratory tract infections in children and for Asthma; <http://www.kaypahoito.fi/web/english/home>]. Thereon, inhaled corticosteroids or leukotriene modifiers are usually administered as intermittent or regular medication to prevent symptoms. However, these medications used to control asthma have, at its best, only modest effect on early childhood wheezing [Castro-Rodriguez et al. 2009]. In addition, daily use of inhaled corticosteroids may affect growth [Kelly et al. 2012]. Accordingly, there is a current need for new therapeutic agents to treat young children with recurrent troublesome lung symptoms.

Effects of tiotropium in the airways

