STATISTICAL POWER OF THE STUDY

The primary endpoint of the study is the proportion (%) of episode-free days in the TBS group, compared with the SA, after a 48-week intervention period. To ensure a 80% power to detect a 15% difference (corresponding to 1 day per week) in episode-free days between the treatment groups, at least 64 children per group were required, assuming a standard deviation of 27% for symptom-free days seen in a previous study [Bisgaard et al. 2006], and a possible drop-out percent of 20%. The calculation is based to reject the primary hypothesis with 5% significancy level.

STATISTICAL ANALYSIS PLAN

Normality of the distribution of continuous variables are to be evaluated by Shapiro-Wilk test. The overall difference between the treatment groups is to be evaluated by using either analysis of variance, Kruskal-Wallis, log-rank, chi-squared, or Fisher's exact tests. Pairwise analyses are to be performed by using Mann-Whitney U, chi-squared, or Fisher's exact tests. Bonferroni correction is to be applied in pairwise analyses by multiplying each P-value by 3. Influence of confounding factors on the primary outcome is to be assessed by conducting the two-way factorial analysis of variance. $P<0.05$ is to be considered statistically significant. All study participants are to be included in safety analyses, and those with diary data available are to be included in primary analysis. All analyses are to be performed as intention-to-treat. IBM SPSS Statistics (version 22.0; Armonk, NY, US) is to be used for all analyses.

RESEARCH METHODS AND MATERIAL, ETHICAL ISSUES

Inclusion criteria:

1. Children at the age of 6 to 35 months.
2. Two to four physician-confirmed episodes of wheeze and/or shortness of breath.
3. Parents/legal representatives with sufficient written and spoken skills in Finnish language

Exclusion criteria:

1. Birth before 36th week of gestation.
2. Suspected/diagnosed chronic parenchymal lung disease or a structural airway defect, or a history of thoracotomy with pulmonary resection.
3. A history of congenital or acquired heart disease, including any unstable or life-threatening cardiac arrhythmia.
4. Constipation with a need of regular medication, or a diagnosed/suspected structural defect in the gastrointestinal tract.
5. A history of malignancy, or other significant chronic disorder, disease, or defect.

Study population and study design

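### The case-by-case withdrawal clause does not say whether an asthma diagnosis counts, and nothing keeps the diary running after withdrawal, so later and probably worse days can go unrecorded

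*Combined protocol and SAP*

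**What the plan says.** Four places in the combined protocol and SAP bear on this.

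- **Study population and study design, the clause.** If a child is "diagnosed a chronic illness needing regular controls and physician care, the investigator will evaluate the situation and considers, case by case, a withdrawal" from the study as a whole, not only from study medication. No illnesses are listed, and asthma is neither named nor exempted.
- **Same section, the next sentences.** The text continues that "hospitalization for wheezing or shortness of breath, or administration of drugs other than the interventional ones are not considered as indications for the discontinuation", because "these occasions are regarded as normal occurrences in early childhood wheezing illnesses". It then adds that "Per oral or inhalant corticosteroids may be used in any of the study groups as additional medications", subject to the national asthma guideline. For a child who does discontinue, the section says how wheeze will be treated but not whether data collection goes on.
- **Handling of data.** "Discontinuation of the study leads to the intention-to-treat analysis of the collected case-specific data".
- **Statistical analysis plan.** All analyses are called intention-to-treat, and "those with diary data available are to be included in primary analysis". No minimum diary length, no denominator for a shortened diary and no method for missing days is given.

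The Objective section defines an episode-free day as one that is, among other things, free of rescue and supplementary controller medication. The power section names the primary comparison as tiotropium plus salbutamol (TBS) against salbutamol alone (SA), over 48 weeks.

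**The concern.** A child whose wheeze worsens during the trial may be admitted, be given inhaled corticosteroids and remain in the study. If the same child is then labelled asthmatic, a literal reading of the clause makes that child a candidate for withdrawal. The exception covers admissions and drugs but does not mention a diagnosis.

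Such a case is foreseeable. The trial enrols children with two to four episodes. The background section places usual controller use at four episodes, or three with risk factors.

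Withdrawal of this kind is linked to the outcome. A child started on a daily supplementary controller would have no episode-free days from then on, by definition. If the diary stops, those failed days become days that are not counted, and the child's proportion rests on the better, earlier part of follow-up.

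The decision is discretionary. No placebo is described, the SA arm has no intermittent controller, and the TBS arm uses a different spacer from the SA arm, so the person deciding would likely know the allocation. Bias in either direction is possible.

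**Working it through.** **The plan's own figure.** With a difference of 15 points, SD 27, two-sided 5% and 80% power, n = 2 × (1.960 + 0.842)² × 27² / 15² = 50.9, rounded up to 51 per group. Allowing 20% drop-out, 51 / 0.8 = 63.75, rounded up to 64. The stated 64 is reproduced, and this point does not change it. The planned 65 per arm leaves 65 × 0.8 = 52 evaluable.

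**Which days are at risk.** Follow-up is 48 × 7 = 336 days. A child withdrawn at mid-study contributes 168 recorded days, and 168 go unrecorded. The recorded days stay in the primary analysis.

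**Bias per withdrawn child.** Assume the proportion is taken over recorded days and withdrawal falls at mid-study. The child is scored at the pre-withdrawal rate instead of the full-period mean, so the overstatement is pre − (pre + post)/2 = (pre − post)/2. Assume a pre-withdrawal rate of 70%:

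- post 70% (stable child): 0 points
- post 50%: 10 points
- post 30%: 20 points
- post 0% (daily supplementary controller): 35 points

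**Bias in the TBS − SA difference** = (share withdrawn in TBS − share withdrawn in SA) × that value. The shares are also assumptions.

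| Withdrawn, SA vs TBS | Stable | Post 50% | Post 30% | Post 0% |
|---|---|---|---|---|
| 15% vs 8% | 0 | −0.7 | −1.4 | −2.45 |
| 20% vs 5% | 0 | −1.5 | −3.0 | −5.25 |

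A milder case has withdrawal in SA only and a later worsening of 13.5 to 27 points (half to one SD). At 5% withdrawn the shrinkage is 0.05 × 13.5/2 = 0.34 to 0.05 × 27/2 = 0.68 points. At 10% it is 0.68 to 1.35 points. If the TBS arm lost more children, the signs would reverse.

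**Effect on power.** With 52 per arm the standard error is 27 × √(2/52) = 5.30, and power is Φ(difference/5.30 − 1.96). This is a normal approximation at an unadjusted 5%, as in the plan's own calculation.

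- no shrinkage (15 points): 81%
- shrinkage 0.7: 77%
- shrinkage 2.45: 66%
- shrinkage 5.25: 45%

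**Dependence on the denominator.** If unrecorded days were instead counted as not episode-free over all 336 days, every child above would score 70 × 168/336 = 35%. That is correct for post 0% but 35 points too low for a stable child. The plan does not say which denominator applies, so even the direction of the error for a given child is open.

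**The case against.** The strongest reply is that the clause was never aimed at asthma. It follows the adverse-event sentence and resembles the exclusion criterion on other significant chronic disorders, so a new comorbidity is a natural reading. The text then exempts wheeze admissions and added drugs, and allows guideline corticosteroids in every group. The plan evidently expects children who need asthma-type treatment to stay. The clause also only asks the investigator to consider withdrawal. All of this is fair. The sentences are a rule and an exception, not a flat contradiction. What remains is that the exception does not mention the diagnosis, and that for any withdrawn child nothing says the diary goes on.

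A reader might infer that the worst outcomes are removed from the primary endpoint. The documents do not support that. The Handling of data section keeps what was collected, and the SAP includes every child with diary data, so only later days are at risk.

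A reader might also take the background statement that "only one third of these infants and toddlers with wheezing will actually develop asthma" as the share exposed to the clause. That figure has no time frame and is not a 48-week rate in this trial, so it cannot size the problem.

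The magnitudes are open to challenge too. Every withdrawal and outcome rate is assumed. Losing 15% to 20% of the SA arm for this one reason would use most or all of the 20% allowed for drop-out from any cause. For children whose rate is stable, the bias is zero.

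**Conclusion.** The concern holds in a limited form. The trigger for withdrawal is undefined with respect to asthma, and the decision rests with someone who would likely know the arm. Because the documents do not provide for follow-up after withdrawal, later days can be lost in a way related to the outcome. Calling the analysis intention-to-treat does not recover days that were never recorded.

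The illustrative shift in the TBS − SA difference is 0 to about 2.5 points. About 5 points, roughly a third of the 15-point target (5.25/15 = 35%), needs 20% against 5% withdrawn, every such child actually withdrawn at mid-study, and no episode-free days afterwards. The range rests on a proportion taken over recorded days and on rates that do not come from the documents. If few children are withdrawn, or the arms lose similar children in similar numbers, the bias is small. The sample size needs no change on this account.

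**What to change.** 1. Reconcile the sentences in the study design section so that they say whether an asthma diagnosis falls under the withdrawal clause. Which way that is settled is a clinical decision and is not proposed here.
2. Separate stopping study treatment from stopping follow-up, so that the first does not by itself end the second.
3. Continue the diary, phone calls and scheduled visits to week 48 for every randomised child unless the caregivers withdraw consent, and include those days in the primary analysis.
4. State the denominator for an incomplete diary and how missing days are handled, with a sensitivity analysis.
5. Tabulate withdrawals and asthma diagnoses by arm, with dates.

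The cost is a wording amendment and continued diary collection in what is likely to be a few children, at visits already scheduled.
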